Appendix 2. Clinical Laboratory Tests

Hematology ^{a,b}	Clinical Chemistry ^{a,b}
Hemoglobin	Serum Concentrations of:
Hematocrit	Sodium
Erythrocyte count (RBC)	Chloride
Mean cell volume	Bicarbonate
Mean cell hemoglobin	Potassium
Mean cell hemoglobin concentration	Total bilirubin
Leukocytes (WBC)	Total protein
Cell morphology	Direct bilirubin
Neutrophils, segmented	Alkaline phosphatase (ALP)
Lymphocytes	Alanine aminotransferase (ALT)
Monocytes	Aspartate aminotransferase (AST)
Eosinophils	Gamma-Glutamyl Transferase (GGT)
Basophils	Blood urea nitrogen (BUN)
Platelets	Creatinine
	Uric acid
	Calcium
	Glucose
	Albumin
	Cholesterol (total)
	Triglycerides
	Lipid Panel (fasting) ^c
	HDL cholesterol
	LDL cholesterol
	Creatine kinase (CK)
	Other Tests^a
	Hepatitis B DNA PCR (if indicated) ^{b,d}
	Pregnancy test (urine) ^e
	FSH ^{b,e}
	CCI
	Anti-mirikizumab antibodies (immunogenicity)
	Serum mirikizumab concentration (PK)
	C-reactive protein, high-sensitivity
	Clostridium difficile ^{f,g} and Stool Cultures
	Fecal calprotectin
	Exploratory cytokines
	Tryptase ^h
	Complement (C3/C4) ^h
	Cytokine panel ^h

Footnotes on next page.

Abbreviations: ADA = anti-drug antibody; anti-HBc+ = positive anti-hepatitis B core antibody;
DNA = deoxyribonucleic acid; FSH = follicle-stimulating hormone; HBsAg- = negative hepatitis B surface antigen; HBV = hepatitis B virus; HDL = high density lipoprotein; LDL = low density lipoprotein
PCR = polymerase chain reaction; PK = pharmacokinetic; RBC = red blood cell; RNA = ribonucleic acid;
SC = subcutaneous; WBC = white blood cell.

^a Assayed by Lilly-designated laboratory.

^b Results will be confirmed by the Central Laboratory/other at the time of initial testing.

^c For the fasting lipid profile, patients should not eat or drink anything except water for 12 hours prior to test.

^d Hepatitis B PCR testing will be performed in patients known from induction study to be HBsAg-, anti-HBc+, and in whom HBV DNA was not detected.

^e Urine pregnancy test will be evaluated locally. FSH test can be performed to confirm that women ≥ 50 years of age with spontaneous amenorrhea for at least 6 months lack childbearing potential, see Inclusion Criteria [4b].

^f To be performed only for patients with secondary loss of response after at least 3 maintenance SC doses to determine eligibility for rescue dosing.

^g Can be done locally by investigator as needed

^h Performed only in the event of systemic allergic/hypersensitivity events, along with ADA and PK.

Appendix 3. Study Governance Considerations

Appendix 3.1. Regulatory and Ethical Considerations, Including the Informed Consent Process

Appendix 3.1.1. Informed Consent

The investigator is responsible for:

- Ensuring that the patient/patient's legal representative understands the nature of the study, the potential risks and benefits of participating in the study, and that their participation is voluntary.
- Ensuring that informed consent is given by each patient or legal representative. This includes obtaining the appropriate signatures and dates on the informed consent form (ICF) prior to the performance of any protocol procedures and prior to the administration of investigational product.
- Answering any questions the patient/patient's legal representative may have throughout the study and sharing in a timely manner any new information that may be relevant to the patient's/patient's legal representative's willingness to continue his or her participation in the study.
- Ensuring that a copy of the ICF is provided to the participant or the participant's legal representative and is kept on file.
- Ensuring that the medical record includes a statement that written informed consent was obtained before the participant was enrolled in the study and the date the written consent was obtained. The authorized person obtaining the informed consent must also sign the ICF.

Appendix 3.1.2. Recruitment

Eli Lilly and Company (Lilly) is responsible for the central recruitment strategy for patients. Individual investigators may have additional local requirements or processes.

Appendix 3.1.3. Ethical Review

The investigator must give assurance that the ethical review board (ERB) was properly constituted and convened as required by International Council for Harmonisation (ICH) guidelines and other applicable laws and regulations.

Documentation of ERB approval of the protocol and the ICF must be provided to Lilly before the study may begin at the investigative site(s). Lilly or its representatives must approve the ICF, including any changes made by the ERB(s), before it is used at the investigative site(s). All ICFs must be compliant with the ICH guideline on Good Clinical Practice (GCP).

The study site's ERB(s) should be provided with the following:

- The protocol and related amendments and addenda, current Investigator Brochure (IB), and updates during the course of the study
- ICF

- Other relevant documents (for example, curricula vitae, advertisements)

Appendix 3.1.4. Regulatory Considerations

This study will be conducted in accordance with the protocol and with the:

- Consensus ethics principles derived from international ethics guidelines, including the Declaration of Helsinki and Council for International Organizations of Medical Sciences (CIOMS) International Ethical Guidelines
- Applicable ICH GCP Guidelines
- Applicable laws and regulations

Some of the obligations of the sponsor will be assigned to a third party.

Appendix 3.1.5. Investigator Information

Physicians with a specialty in gastroenterology will participate as investigators in this clinical trial. Site-specific contact information may be provided in a separate document.

Appendix 3.1.6. Protocol Signatures

The sponsor's responsible medical officer will approve the protocol, confirming that, to the best of his or her knowledge, the protocol accurately describes the planned design and conduct of the study.

After reading the protocol, each principal investigator will sign the protocol signature page and send a copy of the signed page to a Lilly representative.

Appendix 3.1.7. Final Report Signature

The clinical study report (CSR) coordinating investigator will sign the final CSR for this study, indicating agreement that, to the best of his or her knowledge, the report accurately describes the conduct and results of the study.

The CSR coordinating investigator will be selected by the study team. If this investigator is unable to fulfill this function, another investigator will be chosen by Lilly to serve as the CSR coordinating investigator.

The sponsor's responsible medical officer and statistician will approve the final CSR for this study, confirming that, to the best of his or her knowledge, the report accurately describes the conduct and results of the study.

Appendix 3.2. Data Quality Assurance

To ensure accurate, complete, and reliable data, Lilly or its representatives will do the following:

- Provide instructional material to the study sites, as appropriate
- Sponsor start-up training to instruct the investigators and study coordinators. This training will give instruction on the protocol, the completion of the electronic case report forms (eCRFs), and study procedures.

- Make periodic visits to the study site
- Be available for consultation and stay in contact with the study site personnel by mail, telephone, and/or fax
- Review and evaluate eCRF data and use standard computer edits to detect errors in data collection
- Conduct a quality review of the database

In addition, Lilly or its representatives will periodically check a sample of the patient data recorded against source documents at the study site. The study may be audited by Lilly or its representatives, and/or regulatory agencies at any time. Investigators will be given notice before an audit occurs.

The investigator will keep records of all original source data. This might include laboratory tests, medical records, and clinical notes. If requested, the investigator will provide the sponsor, applicable regulatory agencies, and applicable ERBs with direct access to original source documents.

Appendix 3.2.1. Data Capture System

An eCRF system will be used in this study. The site maintains a separate source for the data entered by the site into the sponsor-provided eCRF system. The eCRF data will be encoded and stored in a clinical trial database.

Electronic clinical outcome assessments (eCOA) measures (questionnaires, scales, self-reported diary data, etc.) will be collected by the patients and site personnel at the time that the information is obtained. In these instances, where there is no prior written or electronic source data at the site, the eCOA data record will serve as the source. The eCOA data will be stored at a third party site. Investigator sites will have continuous access to the source documents during the study and will receive an archival copy at the end of the study for retention. Any data for which the eCOA instrument record will serve to collect source data will be identified and documented by each site in that site's study file.

Data managed by a central vendor, such as laboratory test data or endoscopy data, will be stored electronically in the central vendor's database system. Data will subsequently be transferred from the central vendor to the Lilly data warehouse.

Data from complaint forms submitted to Lilly will be encoded and stored in the global product complaint management system.

Appendix 3.3. Study and Site Closure

Appendix 3.3.1. Discontinuation of Study Sites

Study site participation may be discontinued if Lilly or its designee, the investigator, or the ERB of the study site judges it necessary for medical, safety, regulatory, or other reasons consistent with applicable laws, regulations, and GCP.

Appendix 3.3.2. Discontinuation of the Study

The study will be discontinued if Lilly or its designee judges it necessary for medical, safety, regulatory, or other reasons consistent with applicable laws, regulations, and GCP.

Appendix 3.4. Publication Policy

The publication policy for Study I6T-MC-AMBG (AMBG) is described in the letters of agreement between the sponsor and the investigators and institutions.

**Appendix 4. Hepatic Monitoring Tests for
Treatment-Emergent Abnormality**

Selected tests may be obtained in the event of a treatment-emergent hepatic abnormality and may be required in follow-up with patients in consultation with the Lilly, or its designee, clinical research physician. These tests will be performed at a Lilly-designated laboratory.

Hepatic Monitoring Tests

Hepatic Hematology

Hemoglobin
 Hematocrit
 RBCs
 WBCs
 Neutrophils, segmented
 Lymphocytes
 Monocytes
 Eosinophils
 Basophils
 Platelets

Hepatic Chemistry

Total bilirubin
 Direct bilirubin
 Alkaline phosphatase
 ALT
 AST
 GGT
 CPK

Haptoglobin**Hepatic Coagulation**

Prothrombin Time
 Prothrombin Time, INR

Hepatic Serologies^a

Hepatitis A antibody, total
 Hepatitis A antibody, IgM
 Hepatitis B surface antigen
 Hepatitis B surface antibody
 Hepatitis B core antibody
 Hepatitis C antibody
 Hepatitis E antibody, IgG
 Hepatitis E antibody, IgM

Anti-nuclear antibody**Alkaline phosphatase isoenzymes****Anti-smooth muscle antibody (or anti-actin antibody)**

Abbreviations: ALT = alanine aminotransferase; AST = aspartate aminotransferase; CPK = creatinine phosphokinase; GGT = gamma-glutamyl transferase; Ig = immunoglobulin; INR = international normalized ratio; RBC = red blood cell; WBC = white blood cell.

^a Reflex/confirmation dependent on regulatory requirements and/or testing availability.

Appendix 5. Risk Factors for Latent Tuberculosis Infection

Risk Factors for Latent Tuberculosis Infection
Household contact or recent exposure to an active case
Birth or residency in a high burden country (>20/100,000)
Residents and employees of high risk congregate settings, for example, prisons, homelessness, intravenous drug use
Source: Adapted from Horsburgh and Rubin (2011) and Lewinsohn et al. (2017).

Risk Factors for Increased Likelihood of Progression from LTBI to Active TB
Household contact or close contact with an active case
HIV
Radiographic evidence of old, healed TB that was not treated
Silicosis
Treatment with ≥ 15 mg prednisone (or equivalent) per day
Children <5 years of age
Chronic renal failure
Treatment with an anti-TNF antibody
Poorly controlled diabetes
Intravenous drug use
Weight $\geq 10\%$ below normal
Smoking

Abbreviations: HIV = human immunodeficiency virus; LTBI = latent tuberculosis infection; TB = tuberculosis; TNF = tumor necrosis factor.

Source: Adapted from Horsburgh and Rubin (2011).

WHO List of High Burden Countries (as at 28 Oct 2015, includes but may not be limited to)		
Angola	India	Peru
Azerbaijan	Indonesia	Philippines
Bangladesh	Kenya	Russian Federation
Belarus	Kazakhstan	Sierra Leone
Botswana	Democratic People's Republic of Korea	Somalia
Brazil	Kyrgyzstan	South Africa
Cambodia	Lesotho	Swaziland
Cameroon	Liberia	Tajikistan
Central African Republic	Malawi	United Republic of Tanzania
Chad	Republic of Moldova	Thailand
China	Mozambique	Uganda
Congo	Myanmar	Ukraine
Democratic Republic of the Congo	Namibia	Uzbekistan
Ethiopia	Nigeria	Vietnam
Ghana	Pakistan	Zambia
Guinea-Bissau	Papua New Guinea	Zimbabwe

Source: WHO [WWW]

**Appendix 6. Mayo Scoring System for the Assessment of
Ulcerative Colitis Activity**

Stool Frequency (SF) Subscore	Score
Normal number of stools for subject	0
1 to 2 stools more than normal	1
3 to 4 stools more than normal	2
5 or more stools than normal	3
Rectal Bleeding (RB) Subscore	Score
No blood seen	0
Streaks of blood with stool less than half of the time	1
Obvious blood (more than just streaks) or streaks of blood with stool most of the time	2
Blood alone passed	3
Endoscopic Subscore (ES)	Score
Normal or inactive disease	0
Mild disease (erythema, decreased vascular pattern)	1
Moderate disease (marked erythema, absent vascular pattern, friability, erosions)	2
Severe disease (spontaneous bleeding, ulceration)	3
Physician's Global Assessment (PGA)	Score
Normal	0
Mild disease	1
Moderate disease	2
Severe disease	3
Mayo Score = Stool Frequency (SF) + Rectal Bleeding (RB) + Endoscopic Subscore (ES) + Physician's Global Assessment (PGA)	

Note: The Mayo score ranges from 0 to 12, with higher scores indicating more severe disease. Modified Mayo score excludes PGA and ranges from 0 to 9. Composite SF and RB score ranges from 0 to 6. The original description of the Mayo score included friability in the definition of an ES of 1. Consistent with current clinical practice and regulatory guidance, this study excludes friability from the definition of an ES of 1.

Stool frequency reports the number of stools in a 24-hour period, relative to the normal number of stools for that patient. The reference "normal" stool frequency for that patient will be recorded electronically at the screening visit in Study AMAN. The Normal SF refers to when the patient was in remission or, if the patient has never achieved remission, the reported SF before initial onset of signs and symptoms of ulcerative colitis. Remission refers to a period of time since being diagnosed with ulcerative colitis when the patient is not experiencing any signs or symptoms relating to ulcerative colitis. This period of time may last a few weeks or a few months or may even last several years. The patient will record this electronically as source data in the tablet device at the screening study visit in Study AMAN.

Source: Adapted from Schroeder et al. (1987) and Scherl et al. (2009)

Appendix 7. Patient-Reported Outcome Instruments

Daily Diary Review

Rectal Bleeding^a
 Stool Frequency^a
 Urgency NRS^a
 Abdominal Pain NRS^a
 PGRS^a
 Nocturnal Stool^b
 Fatigue NRS^b
 Bristol Stool Scale^b

Abbreviations: NRS = numeric rating scale; PGRS = Patient's Global Rating of Severity

^a Question will be administered daily through Week 40 or early termination visit.

^b Question will be administered at Visits 2 through 10 (Weeks 4 through 36), and daily between Visit 10 and Visit 11.

The following are descriptions of additional patient-reported outcome instruments used in Study AMBG using Patient eDiary or tablet device:

- **Urgency Numeric Rating Scale (NRS):** A single item that measures the severity of the urgency (sudden or immediate need) to have a bowel movement in the past 24 hours, using an 11-point NRS ranging from 0 (no urgency) to 10 (worst possible urgency). Patients will be provided with an electronic diary tool during screening to record information daily pertaining to their severity of urgency.
- **Abdominal Pain NRS:** A single item that measures the “worst abdominal pain in the past 24 hours” using an 11-point NRS ranging from 0 (no pain) to 10 (worst possible pain). Patients will be provided with an electronic diary tool during screening to record information daily pertaining to their worst abdominal pain experience.
- **Patient's Global Rating of Severity (PGRS):** The PGRS is a 1-item patient-rated questionnaire designed to assess the patients' rating of their disease symptom severity over the past 24 hours. Responses are graded on a 6-point scale in which a score of 1 indicates that the patient has no symptoms (that is, “none”) and a score of 6 indicates that the patient's symptom(s) are “very severe.” Patients will be provided with an electronic diary tool during screening to record information daily pertaining to their disease experience.
- **Nocturnal Stool:** The Nocturnal Stool instrument is a single item asking the patient to record the number of stools they had during the night (or day, for shift workers), causing them to waken from sleep. Patients will be provided with an electronic diary tool during screening to record information daily pertaining to their nocturnal stool count during appropriate time periods. Patients will also record their response to the nocturnal stool count electronically as source data in the tablet device at appropriate visits.
- **Fatigue NRS:** The Fatigue NRS is a single item that measures the “worst fatigue (weariness, tiredness) in the past 24 hours” using an 11-point NRS ranging from 0 (no fatigue) to 10 (fatigue as bad as you can imagine). Patients will be provided with an electronic diary tool during screening to record information daily pertaining to their worst fatigue experience during appropriate time periods. Patients will also record their

response to the Fatigue NRS electronically as source data in the tablet device at appropriate visits.

- **Bristol Stool Scale:** The Bristol Stool Scale is a single item that provides a pictorial and verbal description of stool consistency and form, ranging from Type 1 (hard lumps) to Type 7 (watery/liquid). Patients will be provided with an electronic diary tool during screening to record information daily pertaining to their stool during appropriate time periods. Patients will also record their response to the Bristol Stool Scale electronically as source data in the tablet device at appropriate visits.
- **Patient's Global Rating of Change (PGRC):** The PGRC scale is a patient-rated instrument designed to assess the patients' rating of change in their symptom(s). Responses are graded on a 7-point Likert scale, in which a score of 1 indicates that the subject's symptom(s) is "very much better," a score of 4 indicates that the subject's symptom(s) has experienced "no change," and a score of 7 indicates that the subject's symptom(s) is "very much worse." Patients will record their response to the PGRC electronically as source data in the tablet device at appropriate visits.
- **Inflammatory Bowel Disease Questionnaire (IBDQ):** A 32-item patient-completed questionnaire that measures 4 aspects of patients' lives: symptoms directly related to the primary bowel disturbance, systemic symptoms, emotional function, and social function (Guyatt et al. 1989; Irvine et al. 1994, 1996). Responses are graded on a 7-point Likert scale, in which 7 denotes "not a problem at all" and 1 denotes "a very severe problem." Scores range from 32 to 224; a higher score indicates a better quality of life. Patients will record their responses to the IBDQ electronically as source data in the tablet device at appropriate visits.
- **European Quality of Life 5-Dimension 5 Level (EQ-5D 5L):** A widely used, generic questionnaire that assesses health status (Herdman et al. 2011; EuroQol Group 2015). The questionnaire consists of 2 parts. The first part assesses 5 dimensions (mobility, self-care, usual activities, pain/discomfort, and anxiety/depression) that have 5 possible levels of response (no problems, slight problems, moderate problems, severe problems, extreme problems). This part of the EQ-5D can be used to generate a health state index score, which is often used to compute quality-adjusted life years (QALY) for utilization in health economic analyses. The health state index score is calculated based on the responses to the 5 dimensions, providing a single value on a scale from less than 0 (where zero is a health state equivalent to death; negative values are valued as worse than dead) to 1 (perfect health), with higher scores indicating better health utility (EuroQol Group [WWW]). The second part of the questionnaire consists of a visual analog scale (VAS) on which the patient rates their perceived health state from 0 (the worst health you can imagine) to 100 (the best health you can imagine). Patients will record their responses to the EQ-5D 5L electronically as source data in the tablet device at appropriate visits.
- **Medical Outcomes Study 36-Item Short Form Health Survey (SF-36) Version 2:** A patient-reported, generic, health-related quality of life instrument originally published in 1992, with some item wordings and response options revised in 2000 (Ware and Sherbourne 1992; Ware 2000). It consists of 36 questions measuring 8 health domains: physical functioning, bodily pain, role limitations due to physical problems, role

limitations due to emotional problems, general health perceptions, mental health, social function, and vitality. The patient's responses are solicited using Likert scales that vary in length, with 3 – 6 response options per item. The SF-36 can be scored into the 8 health domains named above and 2 overall summary scores: physical component summary (PCS) and mental component summary (MCS) scores. The domain and summary scores range from 0 to 100; higher scores indicate better levels of function and/or better health. The SF-36 version 2 (standard version) will be used, which utilizes the recall period of “the past 4 weeks” (Ware and Sherbourne 1992; Maruish 2011). Patients will record their responses to the SF-36 Version 2 electronically as source data in the tablet device at appropriate visits.

- **Work Productivity and Activity Impairment Questionnaire: Ulcerative Colitis (WPAI:UC):** A patient-reported instrument developed to measure the impact on work productivity and regular activities attributable to a specific health problem (WPAI:UC). It contains 6 items that measure: 1) employment status, 2) hours missed from work due to the specific health problem, 3) hours missed from work for other reasons, 4) hours actually worked, 5) degree health affected productivity while working, and 6) degree health affected productivity in regular unpaid activities. Four scores are calculated from the responses to these 6 items: absenteeism, presenteeism, work productivity loss, and activity impairment (Reilly Associates [WWW]). Scores are calculated as impairment percentages (Reilly et al. 1993), with higher numbers indicating greater impairment and less productivity, that is, worse outcomes (Reilly Associates [WWW]). Patients will record their responses to the WPAI:UC electronically as source data in the tablet device at appropriate visits.

Appendix 8. Prohibited Medications

This section outlines medications that are prohibited during the treatment phase of the study, if applicable. Use of the medications listed in this appendix is allowed at the discretion of the investigator after a patient discontinues study drug and completes the early termination visit.

Drug Class	Comments
Anti-TNF antibodies (for example, infliximab, adalimumab, or golimumab)	Prohibited throughout treatment period
Anti-integrin antibodies (for example, vedolizumab)	Prohibited throughout treatment period
Agents depleting B or T cells (for example, rituximab, alemtuzumab, or visilizumab)	Prohibited throughout treatment period
Immunomodulatory medications, including oral cyclosporine, IV cyclosporine, tacrolimus, mycophenolate mofetil, thalidomide or JAK inhibitors (for example, tofacitinib)	Prohibited throughout treatment period
Rectally administered 5-ASAs (enemas or suppositories)	Prohibited throughout treatment period
Rectally administered corticosteroids (enemas or suppositories)	Prohibited throughout treatment period
Rectally administered investigational preparations for UC such as arsenic preparations	Prohibited throughout treatment period
Intravenous corticosteroids for UC	A course of IV corticosteroids for UC is prohibited
Systemic corticosteroids for non-UC indications (oral or IV)	Patients requiring systemic corticosteroids for non-UC conditions are excluded. Exceptions include corticosteroids to treat adrenal insufficiency, premedication for IP infusion, or locally administered corticosteroids (e.g., inhaled, intranasal, intra-articular, topical) (see Appendix 10)
Oral budesonide standard formulation (that is, not the oral budesonide extended release tablet formulation [budesonide MMX])	Prohibited throughout treatment period.
Any investigational therapy (biologic or nonbiologic)	Prohibited throughout treatment period
Interferon therapy	Prohibited throughout treatment period
Leukocyte apheresis (leukopheresis, for example, Adacolumn)	Prohibited throughout treatment period
Anti-IL12p40 antibodies (for example, ustekinumab [Stelara [®]]) or anti-IL-23p19 antibodies (for example, risankizumab [BI-655066], brazikumab [MEDI-2070], guselkumab [CNTO1959], tildrakizumab [MK-3222]) for any indication, including investigational use	Prohibited throughout treatment period
Bacillus Calmette-Guerin (BCG) vaccine	BCG vaccination prohibited throughout the duration of the study and for 12 months after discontinuation of study drug.
Live attenuated vaccines	Live attenuated vaccines are prohibited throughout the duration of the study and for 3 months after discontinuation of study drug.

Abbreviations: 5-ASA = 5-aminosalicylic; IL = interleukin; IV = intravenous; JAK = Janus Kinase; TNF = tumor necrosis factor; UC = ulcerative colitis.

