6.2. Exclusion Criteria

Patients will be excluded from study enrollment if they meet any of the following criteria at maintenance study baseline, unless specifically defined:

Gastrointestinal Exclusion Criteria

- [6.] Have been diagnosed during the previous induction study AMAN with Crohn's disease or Inflammatory Bowel Disease-Unclassified (IBD-U, formerly known as indeterminate colitis).
- [7.] Have had bowel resection or other surgery for the treatment of UC during the previous induction study AMAN, or are likely to require surgery for the treatment of UC during Study AMBG.
- [8.] Have evidence of colonic dysplasia (including dysplasia in flat mucosa or dysplasia-associated lesion or mass [DALM]) at maintenance baseline (Study AMAN Visit 5 [Week 12] endoscopy) or have been diagnosed with cancer of the gastrointestinal tract during Study AMAN.
- [9.] Have current adenomatous polyps that have not been removed. Once removed, the patient may be eligible for study after confirming no dysplasia or malignancy on local histology report.

Infectious Disease Exclusion

- [10.] Have been diagnosed with clinically important infection including, but not limited to, hepatitis B, hepatitis C, HIV/AIDS, and active tuberculosis (TB) during the induction study AMAN.
- [11.] Have detectable hepatitis B virus (HBV) DNA detected at any time in Study AMAN
- [12.] Have been diagnosed with latent TB during the induction study AMAN and are not willing to comply with completing TB treatment as appropriate.
- [13.] Intend to receive a Bacillus Calmette-Guerin (BCG) vaccination or live attenuated vaccine(s) during the study.

General Exclusion Criteria

- [14.] Initiation of a new prohibited medication (see [Appendix 8](#)) during the induction study AMAN.
- [15.] Presence of a hepatic or hematologic laboratory abnormality prior to Visit 1/Week 0 that would require permanent discontinuation from study drug (see Section [8.1.1](#)).

- [16.] Presence of significant uncontrolled neuropsychiatric disorder or judged at risk of suicide in the opinion of the investigator;

OR

Marked “yes” to Columbia-Suicide Severity Rating Scale (C-SSRS) question 4 or 5 on ideation prior to dosing;

OR

Marked “yes” to C-SSRS suicide behaviors questions prior to dosing at Week 0;

AND

The ideation or behavior occurred within the past month.

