7.7. Concomitant Therapy

All concomitant medications taken during the study must be recorded in the Concomitant Medication eCRF. All patients are encouraged to maintain their usual medication regimens for concomitant conditions or diseases throughout the study, unless those medications are specifically excluded ([Appendix 8](#)).

Patients taking permitted UC concomitant medications, other than oral corticosteroids, are to keep doses stable unless modifications are needed due to AEs, and follow the instructions regarding dose stabilization as detailed in [Appendix 9](#). Patients taking oral corticosteroids are to follow the corticosteroid taper instructions described below. Administration of prohibited UC medications, approved or investigational, constitutes treatment failure. Use of such medications should not be withheld if, in the opinion of the investigator, failure to prescribe them would compromise patient safety. Patients who require a prohibited medication to treat their UC (see [Appendix 8](#)) need to be discontinued from study drug and complete an ETV and post-treatment follow-up visits.

If a concomitant medication is needed to treat an AE or for appropriate medical management, the investigator should base decisions on the patient and clinical factors, considering prohibited medications. Local administration of corticosteroids (for example, intranasal, inhaled, intraarticular) are allowed as required for the management of pre-existing conditions and AEs. A patient who initiates a prohibited medication for a non-UC indication may either discontinue the study drug, or discontinue the prohibited medication.

Use of BCG vaccination is prohibited throughout the duration of the study and for 12 months after discontinuation of study drug. Use of nonlive (killed, inactivated or subunit) vaccinations are allowed for all patients; however, their efficacy with concomitant mirikizumab is unknown. Use of live, attenuated vaccines are prohibited during the study and for 3 months after discontinuation of study drug.

The list of prohibited medications and the list of permitted medications with dose stabilization guidance are provided in [Appendix 8](#) and [Appendix 9](#), respectively.

Corticosteroid Taper

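### Appendix 8 releases every listed product after the early termination visit, yet its own rows and Section 7.7 ban BCG for 12 months and live vaccines for 3 months after study drug stops

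*Protocol*

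**What the plan says.** Appendix 8 of the Protocol opens with two general sentences. The first sets the scope: "This section outlines medications that are prohibited during the treatment phase of the study, if applicable". The second is a release, under which any product "listed in this appendix is allowed at the discretion of the investigator after a patient discontinues study drug and completes the early termination visit".

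The table beneath contains two vaccine rows. For BCG: "BCG vaccination prohibited throughout the duration of the study and for 12 months after discontinuation of study drug". For live attenuated vaccines: "Live attenuated vaccines are prohibited throughout the duration of the study and for 3 months after discontinuation of study drug".

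Section 7.7 repeats both periods in the body of the Protocol: "Use of BCG vaccination is prohibited throughout the duration of the study and for 12 months after discontinuation of study drug", and "Use of live, attenuated vaccines are prohibited during the study and for 3 months after discontinuation of study drug". The same section sends the reader to Appendix 8 for the list of prohibited products.

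Three passages bear on prohibited ulcerative colitis (UC) drugs. Section 7.7 says: "Use of such medications should not be withheld if, in the opinion of the investigator, failure to prescribe them would compromise patient safety". It also requires a patient who needs such a drug to stop study drug and to have an ETV and follow-up visits, but does not give the order of these steps relative to the new drug. Section 8.2 places discontinuation from the study before another effective agent is introduced. Appendix 8 dates its permission from completion of the ETV.

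**The concern.** The release sentence covers everything in the appendix, and the two vaccines are in the appendix. Read as written, an investigator may give either vaccine as soon as study drug has been stopped and the ETV is complete. Read by row, the same investigator must wait 12 or 3 months from stopping. The scope sentence points the same way as the release, because it ends the list's reach with the treatment phase, while both rows run through the whole study and beyond it.

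What is at stake is a safety restriction that the Protocol itself states twice. Sites may apply it differently, and a vaccination soon after the ETV could be recorded as a deviation at one site and as permitted at another. The order of events for prohibited UC drugs is a smaller matter of the same kind.

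**Working it through.** The vaccine question is a comparison of texts; the only arithmetic is the size of the gap.

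**Step 1: when each passage ends the prohibition**

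| Passage | BCG | Live attenuated vaccines |
|---|---|---|
| Appendix 8, scope sentence | end of treatment phase | end of treatment phase |
| Appendix 8, release sentence | study drug stopped and ETV completed | study drug stopped and ETV completed |
| Appendix 8, vaccine row | 12 months after stopping | 3 months after stopping |
| Section 7.7 | 12 months after stopping | 3 months after stopping |

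The rows and Section 7.7 agree with each other. The two opening sentences differ from both. All four are current text rather than entries in the amendment summary.

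**Step 2: conflict inside the study as well as after it.** Section 5.3 ends the study at the last visit or scheduled procedure, and Section 7.8.1 treats post-treatment follow-up as part of participation. Section 5.1 sets that follow-up at no more than 16 weeks. Bans that cover the whole study therefore cover follow-up, whereas the release takes effect before follow-up begins.

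**Step 3: size of the gap.** Let g be the number of weeks from stopping study drug to the ETV. The Protocol does not fix g, so 0 to 4 weeks is assumed. Take 12 months as 52 weeks and 3 months as 13 weeks.

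- BCG: gap = 52 − g. At g = 0 it is 52 weeks; at g = 4 it is 48 weeks.
- Live vaccines: gap = 13 − g. At g = 0 it is 13 weeks; at g = 4 it is 9 weeks.

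**Step 4: order of events for prohibited UC drugs**

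- Section 7.7: treatment is not to be denied where denial would compromise safety; study drug is stopped and an ETV done; order not stated.
- Section 8.2: study discontinuation first, then the new agent.
- Appendix 8: use permitted once the ETV is complete; nothing on whether earlier use is barred in an urgent case.

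The three can be read together, but the sequence has to be inferred.

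**The case against.** The best defence is that a specific row overrides a general preamble. A site checking a vaccine would look at its row, find an explicit period, and find the same period in Section 7.7. That makes an actual misapplication unlikely. It does not remove the contradiction: the Protocol nowhere states that rows take precedence, and the release sentence expressly hands the decision to the investigator.

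A reader might infer several stronger points that the text does not support.

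- *Appendix 8 directly contradicts the Section 7.7 rule on urgent UC treatment.* Appendix 8 says when use is allowed; it does not say that use is allowed only then. Section 7.7 reads naturally as a safety exception to the general ban. What remains is an unclear order.
- *Exclusion [13] leaves the post-treatment period open and should be extended.* The criterion covers patients who "Intend to receive a Bacillus Calmette-Guerin (BCG) vaccination or live attenuated vaccine(s) during the study". The study runs to the end of follow-up, 12 or 16 weeks after the end-of-treatment visit, so the criterion reaches roughly the whole live-vaccine period. Only the later part of the BCG period lies outside it, and an entry criterion narrower than a conduct rule is not a contradiction.
- *The continuous-endpoint analysis must be changed for ETV values taken on prohibited drugs.* Section 10.3.1.1 uses two different terms, rescue dosing with mirikizumab in the nonresponder rule and rescue medication in the repeated-measures rule, and they should not be merged. Section 7.7 already classes use of prohibited UC drugs as treatment failure, and Section 10.3.3.1 counts patients who do not reach Week 40 as nonremitters. Further detail commonly belongs in the SAP, which is not at hand.
- *The gap can be expressed as drug remaining, from the half-life.* Such figures run from the last dose, whereas the disputed permission runs from the ETV, whose timing is not fixed.

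**Conclusion.** The vaccine contradiction stands on the text alone. The opening paragraph of Appendix 8 cannot be true together with two rows of its own table and with Section 7.7. On the assumption that the ETV falls 0 to 4 weeks after stopping, the passages differ by 48 to 52 weeks for BCG and 9 to 13 weeks for live vaccines. The number of patients who might be affected is not given and cannot be derived.

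The order of stopping study drug, completing the ETV and starting a prohibited UC drug is a minor clarification across Sections 7.7 and 8.2 and Appendix 8.

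Neither matter changes power, type I error or the primary estimate. The correction is worth making because it concerns a stated safety restriction. No view is taken here on which vaccine period or which treatment sequence is right.

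**What to change.** Reconcile the opening paragraph of Appendix 8 with its BCG and live-vaccine rows and with Section 7.7, so that one post-treatment period per vaccine reads the same everywhere. If the sponsor confirms the rows, both opening sentences need an explicit exception for the two vaccines, with a pointer to the period in each row.

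At the same time, have Sections 7.7 and 8.2 and Appendix 8 state one order for discontinuation, the ETV and the start of a prohibited UC drug, including how the Section 7.7 safety provision fits with the wording of Appendix 8.

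The cost is a few words of text and a memo to sites. No procedure, sample size or analysis changes, and exclusion [13] can stay as it is.
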